Impact of perinatal depression treatment on child developmental outcomes (*acronym: SHARE-CHILD*)

Protocol submitted to the Committee on Ethics of Research on Human Beings
Human Development Research Foundation

NCT 02658994

April 15, 2016

Principal Investigators:

[name]

Email: [contact]

Landline Number: [contact]

[contact]

[name]

Email: [contact]

[contact]

Landline Number: [contact]

[contact]

Collaborators:

Duke Global Health Institute, Duke University, Durham, USA

University of Liverpool, UK

Table of Contents

1. Background.....	4
2. Aims & Objectives.....	4
3. Methodology.....	5
3.1 Study Duration & Area	5
3.2 Data Management	7
3.3 Description of Measures	8
3.4 Similar Research	8
4. Dissemination and Utilization of Results.....	9
5. Ethical Considerations.....	9
6. Annexes.....	10
6.1 Information Sheet	10
6.2 Consent Form	10
6.3 CV of PIs	10

1. Background

Maternal depression is a serious disorder, which affects 20-30% women in low-income countries, is a known risk factor for impaired child development and long-lasting negative consequences on the child. Specifically, the increased risk of mental health problems in the child persists over the life course and is again transmitted to the next generation. The degree to which they causally shift the child's socio-emotional, cognitive, and physical development trajectory is less well understood.

The purpose of our project is to examine whether the successful perinatal depression intervention among mothers leads to improved developmental outcomes in the children from 3 months to 36 months.

2. Aims & Objectives

SHARE CHILD will be nested within an ongoing research program i.e. SHARE- THPP (Thinking Healthy Program delivered by peer volunteers), spearheaded by SHARE (the South Asian Hub for Advocacy, Research and Education on mental health).

SHARE is a collaborative network that is composed of the following: Human Development Research Foundation (Pakistan); Health Services Academy(Pakistan); Institute of Psychiatry (Pakistan); London School of Hygiene and Tropical Medicine and Institute of Psychiatry (UK); University of Liverpool (UK); Public Health Foundation India (India); Sangath (India); Johns Hopkins Bloomberg School of Public Health (US); And a dozen of network of NGOs spread across India, Afghanistan, Nepal, Bangladesh and Sri Lanka.

The broad, long range goal of SHARE is to establish a collaborative network of institutions in South Asia, to carry out and to utilize research that answers policy relevant questions related to reducing the treatment gap for mental disorders in the region. SHARE aims to be a driver to facilitate evidence-based mental health policy and program implementation in one of the world's most populous regions with weak health systems and poor social development indicators.

As a result of this collaborative network currently HDRF in partnership Sangath (India) are to implement an RCT (Randomized Control Trial) study coined "SHARE – THPP (Thinking Healthy Program implemented by peer volunteers)."

The goal of this study is to rigorously evaluate the impact of SHARE THPP perinatal depression intervention delivered by peers that starts prenatally and continues through 6 months post-partum, on child development. We will achieve this by conducting a cohort study that is integrated with the intervention clustered RCT, also being implemented by HDRF.

The SHARE THPP includes individual and community-wide components and follows mothers with prenatal depression until 6 months postpartum. Our project, SHARE CHILD, builds on this trial in several critical ways. We (1) focus on child outcomes, (2) extend follow-up to 36 months postpartum, and (3) investigate factors that mediate and modify the effect of the intervention on child outcomes. A unique

window of opportunity is made possible due to the summer 2014 enrollment start date of the SHARE trial.

In addition to enrolling the depressed women who will participate in the SHARE trial, we will also enroll a control group of non-depressed women, and follow-up the mother-child dyads for at least 36 months post-partum. Enrolling the non-depressed mothers enables us to determine the extent to which the intervention can lead to equivalence between the treated depressed and non-depressed groups as well as to identify potential positive externalities to non-depressed women in the intervention arm.

The overall goal of the project is to follow-up families that participated in the SHARE THPP intervention and see whether the intervention has a positive impact on the cognitive and socioemotional development of their children. This larger goal can be broken down into the following objectives:

1. Enroll SHARE THP study participants and perinatally non-depressed women.
2. Assess developmental outcomes together with potential mediators and moderators up to 36 months.
3. Identify effect size of SHARE THPP intervention on child development and disseminate findings.

[figure not shown]
3. Methodology

3.1 Study Duration & Area

The total duration of the project will be 5 years (starting in April 2014 till April 2019). The study area will be Kallar Syedan, one of the 7 sub-districts of the District Rawalpindi, Pakistan.

The study population is based in rural and peri-urban areas in Rawalpindi, Pakistan. Eligible participants will be women between 16-40 years old, married, in their last trimester of pregnancy and intending to reside in the area for the duration of the study. The intervention utilizes a cluster RCT design with randomization at the Union Council level (administrative unit of approximately 2,500 people). Twenty clusters each will be randomized to the intervention and control arms. The two arms will be further subdivided into non-depressed and depressed women to yield four arms. Our target is to enroll 280 women in each of the four study arms (1,120 mother-child dyads total) and then follow them regularly until the child is 36 months of age. Due to attrition and loss to follow-up, we anticipate that 220 mother-child dyads in each of the four arms will complete the study. Total anticipated enrollment will be 1,120 (see Figure 1).

Figure 1. SHARE CHILD study design in relation to the Parent RCT Intervention.
N=mother-child dyad. Shaded area unique to SHARE CHILD study.

The sampling unit within each cluster is the mother-child dyad. Women in the last trimester of pregnancy residing in one of the 40 study clusters will be identified through community surveillance normally conducted by community health workers (CHW). CHWs are utilized in most lower/middle income countries to deliver basic maternal and child health services. In Pakistan, each CHW covers 100 households and is informed of every pregnancy. Our research team has a long-standing relationship with the CHWs in the study areas. The CHWs will liaise with the research field staff which will seek informed consent from the pregnant woman and screen her for depression using the PHQ-9. We will offer enrollment to each woman who screens positive for depression and the first woman who subsequently screens negative. As a result, every cluster in the intervention and control arms will include women who score above and below the depression screening cutoff. Due to the community nature of the intervention, we anticipate that non-depressed women in the intervention clusters will benefit from the trial. Women who are suicidal, psychotic or already under depression treatment will be referred to mental health specialist care and excluded from the study. If the infant is born with congenital abnormalities or with other significant health problems, the mother-child dyad will be excluded.

Our data collection protocols that begin prenatally through 6 months postpartum will be synchronized with the main SHARE study (see Figure 1). After 6 months, SHARE ends and we continue the SHARE CHILD data collection. Interviews will be scheduled at 3, 6, 12, 24 and 36 postpartum month milestones for each mother-child dyad (see Table 1).

Table 1: Timeline of SHARE CHILD assessments

Breastfeeding		✓	✓	✓		
MSPSS	✓	✓	✓	✓	✓	✓
PHQ-9	✓	✓	✓			
WHO-DAS	✓	✓	✓			
Sociodemographic questions	✓			✓	✓	✓
BAYLEY				✓	✓	✓
HOME		✓	✓	✓	✓	✓
ASQ SE			✓	✓	✓	✓
Vineland			✓	✓	✓	✓
Height/Weight		✓	✓	✓	✓	✓
Maternal postnatal attachment		✓	✓			
Maternal efficacy		✓	✓			
Cohen PSS		✓	✓	✓	✓	✓
IPV	✓	✓		✓	✓	✓
CISR		✓	✓			✓
SDQ						✓
Risk game	✓			✓		
Stroop test	✓			✓		
Autonomy questions	✓			✓	✓	✓
A day in life		✓	✓			
Father involvement in child care	✓	✓	✓	✓	✓	✓

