2.3 Randomization

Within each of the 11 union councils of the sub-district, village clusters were randomized to Intervention or Usual Care control using a 1:1 allocation ratio. Randomization was done before the participants were recruited. Research teams responsible for identifying, obtaining consent and recruiting trial participants were blind to the allocation status (to minimize the post-randomization recruitment bias). Randomization was stratified by union councils, to help minimize the imbalance between arms by factors likely to be associated with the primary outcome and reduce the between-cluster variability, hence increasing the power of the study. Allocation of clusters was carried out by an independent statistician based at the London School of Hygiene and Tropical Medicine (LSHTM) using a computerized randomization sequence.

The trial PI, site PIs/coordinators, trial statisticians and members of the Trial Steering Committee were blinded to the allocation status until the analysis of the six-month data for the parent trial, SHARE.

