2.4 Sample size calculation

Much of the following is copied or adapted from the THPP+ protocol paper.¹

The primary power calculations for the THPP+ study are for the c-RCT comparisons of perinatally depressed women and their children in the control vs. intervention arms at 36 months postnatally at the 5% two-tailed significance level. As with the THPP trial,² we assume 40 village clusters randomized in a 1:1 allocation ratio within 11 union councils with 14 perinatally depressed women per village cluster to yield a total sample size of 560 perinatally depressed women at baseline. In addition, for THPP+, we recruit 14 perinatally non-depressed women per village cluster for a total of 560 perinatally non-depressed women at baseline. We conservatively estimate that loss to follow-up (including infant mortality and maternal illness and death) of both perinatally depressed and perinatally non-depressed women at 36 months will be 20%. Therefore, the total sample size available at 36 months is anticipated to be 480 perinatally depressed and 480 perinatally non-depressed women and their children. Using standard formulae^{3,4} for a cluster randomized design and assuming intra-cluster correlation of 0.07 in the intervention arm and 0.05 in the control arm, the trial will have 90% power at 36 months to detect a difference in perinatally depression remission of 65% in perinatally depressed-Intervention vs. 45% in perinatally depressed-control for the anticipated total sample size of 480 perinatally depressed women at 36 months. For child outcomes, this sample size will yield power of more than 90% to detect a difference between arms in mean total difficulties (TD) score (range 0-40) of 3 points for children of perinatally depressed mothers using plausible estimates for intra-cluster correlations of 0.04-0.08⁵ and 5.2 for standard deviation for the TD score among 3 year olds.⁶

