2.5 Intervention

The intervention for moderate-severe perinatal depression being assessed in these trials was the Thinking Healthy Program Peer-Delivered (THPP). THPP is the adapted version (peer-delivered) of the Thinking Healthy Program (THP) originally developed and evaluated (based on delivery by government-

employed LHWs) in Pakistan.⁹ THP has recently been adopted by the World Health Organization (WHO) for global implementation (http://www.who.int/mental_health/maternal-child/thinking_healthy/en/).

THPP comprises up to 14 sessions. The core strategies used by the peers are: active listening, collaboration with the family, guided discovery, homework, and behavioral (patient) activation (identifying and replacing unhealthy behaviors with healthy ones and practicing them).

The intervention begins in the third trimester of pregnancy, and includes ten home-based individual face-to-face sessions and four group-based sessions (given in the LHW women's group meetings) until the sixth month postnatally. Part of the task sharing by peers is to assist LHWs in organizing and conducting these mandatory routine women's groups and to encourage trial participants to attend these sessions. The following description comes from Atif et al. (2019).¹⁰

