3.1 Analysis of primary and secondary outcomes

The primary analyses are designed as intention-to-treat and will be conducted using Stata version 16. Maternal and child outcomes are listed in Table 1. ***For all outcomes, the 36-month time point is considered primary.*** The primary child outcome is the Total Difficulties score from the Strengths and Difficulties Questionnaire (SDQ-TD). The primary maternal outcome is the Patient Health Questionnaire (PHQ-9). The secondary outcomes are detailed in Table 1. Of note, the Bayley scores (secondary outcome) will be scaled using the provided U.S. normed scales.

Separate outcome analysis will be conducted for mothers and for children. In both cases, data from perinataly depressed (by intervention arm) and perinataly non-depressed participants will be analysed jointly using linear mixed effects models so that all comparisons of interest can be estimated from the same model. The **identity link** will be used for **continuous outcomes** in order to estimate differences in mean outcomes.

Since our main predictor of interest is the treatment arm indicator (with non-depressed as a separate “arm”), which is related to the sampling variable, the primary analyses will be unweighted, and we will use restricted maximum likelihood (REML). If the model fails to converge after 50 iterations, then we use maximum likelihood. In addition, the between-within method will be used to apply small-sample corrections in the mixed effects framework.¹³ The reason for not using the sampling weights is that the sampling scheme is related to the main predictor of interest, so weighting should lead to minimal, if any, changes in the main results of interest. In addition, not using the sampling weights simplifies the modeling process and allows us to use estimation procedures (REML) shown to reduce bias, in addition to allowing us to use small-sample corrections on the models.

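### The protocol removes whole mother-child dyads for the infant's condition at birth, after randomisation and the start of treatment, and the intention-to-treat SAP neither adopts nor withdraws that rule

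*Protocol*

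**What the plan says.** The protocol (3.1) takes the dyad as its unit: "The sampling unit within each cluster is the mother-child dyad". Women enter before birth: "Women in the last trimester of pregnancy residing in one of the 40 study clusters will be identified through community surveillance". It then states: "If the infant is born with congenital abnormalities or with other significant health problems, the mother-child dyad will be excluded". The unit removed is the dyad ("the mother-child dyad will be excluded"), not the child alone. The second trigger is not defined, and the protocol does not say who applies the rule.

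The SAP fixes the order of events. On allocation (2.3): "Randomization was done before the participants were recruited". On treatment (2.5): "The intervention begins in the third trimester of pregnancy".

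On analysis (SAP 3.1): "The primary analyses are designed as intention-to-treat". The same section plans separate analyses for mothers and children. The primary outcomes are the PHQ-9 for mothers and the SDQ total difficulties (TD) score for children, with 36 months as the primary time point. Missing outcomes are handled by complete cases with covariate adjustment, and by pattern-mixture sensitivity analyses if data seem to be missing not at random.

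The 20% attrition allowance (SAP 2.4) is for "loss to follow-up (including infant mortality and maternal illness and death"; exclusion for infant health is not named. The SAP does not mention the protocol's exclusion rule and defines no analysis set.

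**The concern.** A condition seen only at birth cannot be a baseline criterion when randomisation, enrolment and treatment all come first. Removing dyads for it means that the analysed set is no longer the enrolled set, and the two sets may differ by arm.

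Two features make this more than a formality.

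- **The mother leaves with the child.** Her PHQ-9 does not depend on child data, and mothers of sick infants may well be more depressed than average.
- **The second trigger is open-ended.** What counts, who decides and whether that person is blind to arm are all unstated. Mothers know their arm, and intervention mothers receive home-based peer sessions, so a problem could be noticed or reported differently by arm. Child growth is itself a listed outcome, so the rule may select on something close to what the trial measures.

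Dyads removed by rule may also never be counted as missing. In that case neither the complete-case argument nor the pattern-mixture analyses would reach them.

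**Working it through.** **1. Order of events.** The sequence runs: clusters randomised (SAP 2.3), woman enrolled in the last trimester (protocol 3.1), intervention starts in the third trimester (SAP 2.5), birth, exclusion of the dyad (protocol 3.1). The conflict with the intention-to-treat statement follows from this order and needs no arithmetic. The plan states no figure for these exclusions, so the sizes below rest on assumed rates.

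**2. Remission difference.** From SAP 2.4: 65% against 45% remission, 560 depressed women (280 per arm). Assumed: share excluded f of 3-6% (intervention) and 5-10% (control); remission among excluded mothers d = 15 to 25 points below their arm's overall rate p, with the same d in both arms.

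Remission among those kept = [p - f(p - d)]/(1 - f) = p + f·d/(1 - f). Bias in the difference = d·[fI/(1 - fI) - fC/(1 - fC)].

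| fI / fC | d = 15: bias, difference | d = 25: bias, difference |
|---|---|---|
| 3% / 5% | -0.33, 19.67 | -0.54, 19.46 |
| 3% / 10% | -1.20, 18.80 | -2.00, 18.00 |
| 6% / 5% | +0.17, 20.17 | +0.28, 20.28 |
| 6% / 10% | -0.71, 19.29 | -1.18, 18.82 |

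The range is 18.0 to 20.3 points, and the sign is not fixed. If d may also differ by arm, it widens to 20 + 0.46 - 2.78 = 17.7 (3% with d = 15 against 10% with d = 25) and 20 + 1.60 - 0.79 = 20.8 (6% with d = 25 against 5% with d = 15). With equal f and equal d the bias is zero.

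Cross-check at lower rates with no true effect (45% in both arms): excluding 1% against 5%, with none of the excluded remitting, gives 0.45/0.99 - 0.45/0.95 = -1.9 points. With 2% against 4% and 20% remission among the excluded it is -0.5 points.

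**3. SDQ-TD.** Assumed: excluded children score 3 to 5 points above the children kept, equally in both arms. The mean among those kept is the overall mean minus f times that excess, so the bias in intervention minus control = (fC - fI) × excess. The extremes are (0.10 - 0.03) × 5 = +0.35 and (0.05 - 0.06) × 5 = -0.05. Against the planned 3-point benefit, +0.35 shrinks the effect to 2.65 and -0.05 enlarges it to 3.05.

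**4. Numbers and power.** Excluded depressed women: 280 × (0.03 + 0.05) = 22 to 280 × (0.06 + 0.10) = 45.

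Power = Φ(√[(c - 1)/V]·|p1 - p0| - 1.96), where V = [p1(1 - p1)(1 + (m - 1)ρ1) + p0(1 - p0)(1 + (m - 1)ρ0)]/m, with c = 20 clusters per arm and ICCs 0.07 and 0.05 from SAP 2.4. At 480 women (m = 12), V = (0.2275 × 1.77 + 0.2475 × 1.55)/12 = 0.0655 and power is 92.6%, against the 90% stated. Because 20% loss from 560 leaves 448 rather than 480, both starting points are shown.

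| Excluded | From 480 | From 448 |
|---|---|---|
| 0% | 92.6% | 91.6% |
| 5% | 91.9% | 90.8% |
| 10% | 91.0% | 89.9% |

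The loss of power is small throughout.

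**The case against.** The best defence is that the two documents do different jobs. The rule sits in the 2016 child-outcomes protocol, whose Table 1 appears to schedule the PHQ-9 only at the first three time points. The 36-month maternal primary outcome comes from the 2019 SAP, which does not carry the rule over, says it follows the same sample of depressed women, counts even infant death as loss to follow-up, and analyses mothers separately. A reader might infer that mothers were in fact dropped from the PHQ-9 analysis; the documents do not say so. What stands is that nothing withdraws the rule, and the SAP must say which applies.

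A reader might also infer that unblinded staff made the exclusions. The documents do not support that. SAP 2.3 blinds the recruiting teams, and blinds the investigators, coordinators and statisticians until the parent trial's six-month analysis; protocol 3.2 blinds the interviewers. What stands is that the person applying this rule is not named.

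Nor can the whole rule be treated as open to influence by treatment. The trigger is the infant's state at birth, and a psychosocial programme starting in the third trimester is unlikely to change how often congenital abnormalities occur. The undefined second clause is the weak part.

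Some cover exists. The SAP commits to CONSORT and to a flow chart from recruitment to 36 months, and its attrition list is not exhaustive. Neither says that these exclusions will be shown by arm. Finally, restricting child outcomes to infants without such conditions is a defensible target population, provided it is labelled as such.

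**Conclusion.** The conflict is real: a stated rule removes enrolled dyads after randomisation and after treatment has begun, under a plan described as intention-to-treat. Loss of mothers from the PHQ-9 analysis is conditional on the rule being applied as written.

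Material bias is not shown. Under the assumed rates and a common deficit, the remission difference of 20 points moves to between 18.0 and 20.3, and the SDQ-TD bias lies between -0.05 and +0.35 points. It would be tempting to say that the rule favours one arm, but the direction depends on which arm excludes more. More detection through home visits would raise exclusions in the intervention arm, while a health benefit would lower them. Bias is about zero if exclusions are equal by arm and excluded dyads fare alike. The rates, remission deficits and SDQ excess are all assumptions. The point should be corrected because the remedy is cheap, not because the trial's conclusion is likely to turn on it.

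**What to change.** Reconcile protocol 3.1 with SAP 3.1 by defining the analysis sets:

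- **Mothers:** every enrolled mother with 36-month data stays in the PHQ-9 and other maternal analyses, whatever the infant's health.
- **Children:** include all children with 36-month data, and add a labelled sensitivity analysis without those who met the infant-health criterion. If the restriction is kept as the target population, report both and do not call the restricted analysis intention-to-treat.
- **Reporting:** define the second clause as it was applied. Show these exclusions by arm in the flow chart, with the reason and whether whoever decided was blind to arm.

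The cost is SAP wording, one extra analysis and slightly more SDQ variance. The SAP is dated October 2019, after trial conduct ended in August 2019, so the change uses data already collected and adds no visits. Dyads with no 36-month data because of the rule cannot be recovered, but they can be counted and reported.

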3.2 Data Management

Five bachelor/masters' level behavioral scientists or psychologists will be employed jointly by the SHARE and SHARE CHILD studies to conduct all interviews under the direct supervision of [name], PI of the Pakistan site. These interviewers will receive extensive initial and ongoing training. Enrolled mothers will not be blind to depression status or intervention arm; interviewers will be blind and families will be instructed not to disclose maternal depression or intervention status.

Depression will be assessed through the Revised Clinical Interview Schedule (CIS-R).⁵⁵ The CIS-R is a gold standard instrument for assessing psychopathology in community settings and has been widely used in both rich and poor countries. It assesses 14 non-psychotic symptoms that can be mapped to ICD-10 diagnoses. In addition, functional limitations related to mental health at all time points will be assessed with the World Health Organization Disability Assessment Schedule (WHO-DAS).

Confidentiality of all data collected will be maintained at all times. All the data from individuals will be given codes to ensure anonymity, that is mother-infant pairs will be identified by unique ID numbers. All questionnaires, handwritten field notes, transcripts and tape recordings will be kept securely. The database of the SHARE CHILD will be stored on computers, which are security protected, with password access only by senior project staff. Data will be kept confidential and accessible only to the senior project staff.

